4.1.2. Trial Procedures

All on-study procedures are permitted within the time window indicated in the Schedule of Assessments ([Table 2](#)).

4.1.2.1. Screening

The following screening procedures must be performed within 28 days prior to the first day of study therapy unless indicated. Qualifying hematology, serum chemistry (including thyroid-stimulating hormone [TSH] testing), coagulation, physical examination, ECG, and urinalysis collected within 7 days of Cycle 1 Day 1 (C1D1) do not need to be repeated. The following will be performed according to the Schedule of Assessments ([Table 2](#)).

- Patient signature and date on current Institutional Review Board (IRB)-approved informed consent form - Prior to undergoing any study-specific procedure, patients must read, sign, and date the current IRB)-approved informed consent form. Patients may sign consent prior to the 28-day screening period.
- Medical history, baseline signs and symptoms, drug allergies, primary diagnosis, and demographics
- Physical examination, including examination of all major body systems, ECOG performance status, and vital signs - The patient's height will be obtained only at this Screening visit.

- Hematology, coagulation (prothrombin time and INR), and serum chemistry (including liver function tests and TSH) to be performed locally
- Hepatitis B and C serology will be done for all patients.
- Urinalysis to be performed locally - Microscopic analysis and/or urine protein-creatinine ratio (UPCR) should be performed as clinically indicated.
- CT or MRI scans of abdomen and pelvis to rule out metastatic disease. (within 3 months)
- Bone scans are to be performed if metastases to bone are suspected at screening (within 3 months) and to rule out bone metastases.
- Single tracing 12-Lead ECG (QT, PR, and QRS intervals and heart rate will be captured)
- Assessment of concomitant medications and treatments from 28 days prior to the start of study treatment
- Pre-operative baseline core tumor biopsy - Archival Tumor Tissue Specimens: Archival specimens (formalin-fixed, paraffin-embedded) of the primary cancer specimen for each study participant. It is preferable that the entire paraffin block be submitted, but if this is not feasible, then at least 20 unstained slides are requested for immunohistochemical and molecular analysis (sections of ~ 5 microns are preferred).

4.1.2.2. Study Drug Treatment Period

Qualifying hematology, blood chemistry (including TSH testing), coagulation, urinalysis, physical examination, and ECG test do not need to be repeated on C1D1 if acceptable screening assessments are performed within 7 days prior to the start of study therapy. On days of dosing, all assessments should be performed prior to dosing with Abemaciclib unless otherwise indicated in the Schedule of Assessments ([Table 2](#)). Patients will be eligible to receive Abemaciclib until unacceptable toxicity, withdrawal of consent, progression of disease or end of study. Each cycle is 28 days in duration (+/- 3 days). The following will be performed according to the Schedule of Assessments ([Table 2](#)).

- Physical examination including examination of all major body systems, ECOG performance status, weight, and vital signs (heart rate, temperature, blood pressure, respiratory rate)
- Hematology, coagulation (prothrombin time and INR) and serum chemistry (including liver function tests and TSH) to be performed locally
- Urinalysis to be performed locally - Microscopic analysis and/or UPCR should be performed as clinically indicated.
- Administration of Abemaciclib: Abemaciclib will be administered at a dose of 150 mg twice daily and it is provided as 50-mg tablets. Abemaciclib should be taken twice daily (with at least 6-hour separating doses) at the same time each day with a glass of water. Patients should be instructed to swallow tablets whole and not open, chew, or crush. Intrasubject dose escalation of Abemaciclib is not permitted. Abemaciclib will be briefly

stopped 2 weeks prior to radiation therapy and will be restarted a month after radiation therapy is completed. Abemaciclib may be given up to a maximum of 24 months.

- Administration of ADT: Administer ADT as given in standard of care dosing on C1D1 along with Abemaciclib. ADT is given every 3 months. The maximum treatment duration with ADT is 24 months
- Radiation Therapy: This is administered after 2 and half cycles of Abemaciclib and ADT regimen. RT will be given as administered standard of care at the institution – 180 cGy x 28 fractions to the whole pelvis and boost to prostate with 250 cGy x 28 fractions. After RT is completed, both ADT and Abemaciclib are resumed and can be continued up to 24 months. See **Section 6.3 and Appendix 3: UAB Department of Radiation Oncology Treatment Practice Guidelines** for further details of radiation therapy.
- Assessment of adverse events (AEs)
- Assessment of concomitant medications and concomitant treatments

4.1.3. Follow-up

Safety Follow-up

All subjects will complete a safety follow-up visit approximately 30 (+7) days after the last dose of study treatment. Serious adverse events and any concomitant medications associated with serious adverse events observed by the investigators or reported by the subjects that occur through 90 (+7) days after the cessation of all study treatment or 30 (+7) days following cessation of treatment if the subject initiates new anticancer therapy, whichever is earlier, will be reported to Eli Lilly and recorded in the CRF.

Long-term Follow-up

After the safety follow-up visit, all subjects will enter the long-term follow-up. Subjects will be followed for survival and subsequent anticancer therapies every 12 weeks (\pm 28 days) **from safety follow-up** for approximately 12 months after the end of treatment. In addition, Abemaciclib related adverse events that occur through the end of the long-term follow-up will be reported.

For subjects who discontinue study treatment without documented PD and have not **initiated a new** anticancer therapy, every effort should be made to continue monitoring tumor response status by clinical and radiographic tumor assessments.

Table 2: Schedule of Assessments

Protocol Activities	Screening	Cycle 1 (28 days)	Cycle 2-3 (+/- 3 days)	Cycle 4 onwards^h (+/-3days)	EOT/Follow up^a
	Day -28	Day 1	Day 1	Day 1	
Baseline Documentation					
Informed Consent	X				
Medical/Oncology History	X				X
Baseline Signs and Symptoms	X				
Physical Examination	X	X	X	X	X
Vital Signs	X	X	X	X	X
Laboratory Studiesⁱ					
PSA (at screening, prior to RT, and q month after RT) ⁱ	X	X	X	X	X
Hematology ⁱ	X	X	X	X	X
Coagulation ⁱ	X	X			
Blood Chemistry including LFTs ⁱ	X	X	X	X	X
Serology for Hepatitis B and C	X				
Urinalysis	X	X	X	X	
Testosterone level to confirm chemical castration	X		X	X	
Treatment with Study Drug					
Abemaciclib Dosing ^b		X	X ^g	X	

Protocol Activities	Screening	Cycle 1 (28 days)	Cycle 2-3 (+/- 3 days)	Cycle 4 onwards ^h (+/-3days)	EOT/Follow up ^a
	Day -28	Day 1	Day 1	Day 1	
LHRH analogues (SC) ^c		X			
RT			X ^e		
Tumor Assessments					
CT or MRI Scans	X ^f				X ^f
Other Clinical Assessments					
12-Lead ECG	X	X			X
Concomitant Medications/Treatments	X	X	X	X	X
Adverse Events		X	X	X	
Special Laboratory Assessments					
Optional Tumor Biopsy ^d			X ^d		
Archival Tumor Tissue	X				

- a. Refer Section 4.1.3 for frequency of follow-up (safety and long-term).
- b. BID PO dosing Abemaciclib. Abemaciclib will be stopped 2 weeks before RT and will be resumed 1 month after RT.
- c. LHRH analogues will be administered on C1D1 and continued every 3 months for a maximum of 24 months.
- d. An optional MRI-TRUS guided biopsy will be performed at 6 months post radiotherapy,
- e. Radiotherapy will be started after 3 months of start of abemaciclib and ADT.
- f. CT scan or MRI scan will be done to rule out metastatic disease (within 3 months). It will be conducted again at the time of PSA rise (biochemical failure).
- g. Abemaciclib will be stopped 2 weeks before scheduled RT. It will be administered for half a cycle in cycle 3.

- h. Abemaciclib and ADT will be resumed after 1 month of completing RT. This will be counted as 4th cycle and future cycles will continue monthly for Abemaciclib. ADT will be given quarterly. Study treatment will continue until patient progresses, has toxicities or withdraws from study.
- i. Laboratory Studies: The first 2 cycles, labs will be drawn every 2 weeks and may be drawn at outside lab at the PI's discretion.

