definitive RT+ADT. Simon's optimal two-stage design (Simon, 1989) will be used for conducting the trial. The null hypothesis is that the proportion of patients with PSA <0.5 without any treatment is 5%, and the alternative hypothesis is that the proportion of patient with PSA <0.5 at 6 weeks into treatment is 30% or higher. The trial is carried out in two stages. In stage I, a total number of 5 patients is accrued. If there are 0 response (PSA < 0.5) among these 5 patients, the study will be early stopped. Otherwise, additional 18 patients will be accrued in stage II, resulting in a total number sample size of 23. If there are 4 or more responses (PSA < 0.5) among these 23 patients, we reject the null hypothesis and claim that the treatment is promising. The design controls the type I error rate at one-sided 0.025 and yields the power of 80%. If we reject the null hypothesis, seven additional patients will be enrolled to explore the association between biomarkers and clinical activities. Patients receive ADT x 2 years and will start 3 months before RT. Abemaciclib will start with initiation of ADT and pause 2 weeks prior to start of RT. Abemaciclib will resume with the first ADT administration post-radiation, which typically is at 1 month post radiation therapy. Abemaciclib and ADT will continue for a total ADT period of 24 months. Patients will have laboratory evaluation every 2 weeks for the first 2 months and monthly thereafter for the next 2 months. Patients are also seen and evaluated every 4 weeks with laboratory evaluation. Labs may be drawn at outside laboratories at the PI's discretion. For toxicity or adverse event, patients will undergo labs, physical examination and grades of toxicities will be determined using NCI CTCAE version 4.03. Disease response and biochemical failure will be assessed by PSA prior to the start of radiation and every 3 months following the end of radiotherapy and by the investigator (physical exam). The determination of disease progression for the study requires a confirmation of 3 consecutive rises of PSA 3 months apart in the setting of testosterone recovery. Patients will be withdrawn from study for following toxicities,

Toxicity Category	Drug-Related Toxicity/Grade
Hematologic	Grade 4 neutropenia for ≥ 5 days
	Febrile neutropenia: ANC < 1000/mm ³ with a single temperature of $>38.3^{\circ}\text{C}$ (101°F) or a sustained temperature of $\geq 38^{\circ}\text{C}$ (100.4°F) for more than one hour.

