6.2. Description of Androgen Deprivation Therapy

The commonly used preparations are listed below. However any of the other preparations with FDA approval, that result in androgen suppression are acceptable.

Goserelin acetate implant (Zoladex®) / Leuprolide (Lupron)

a. PHARMACOLOGY

Mechanism of Action: Following initial administration in males, goserelin causes an initial increase in serum luteinizing hormone (LH) and follicle stimulating hormone (FSH) levels with subsequent increases in serum levels of testosterone. Chronic administration of goserelin leads to sustained suppression of pituitary gonadotropins, and serum levels of testosterone consequently fall into the range normally seen in surgically castrated men approximately 2-4 weeks after initiation of therapy.

b. PHARMACOKINETICS

1. Absorption: Goserelin 3.6 mg is released slowly in first 8 days, and then rapid and continuous release for the remainder of the 28 day dosing period. Time to peak concentration for goserelin 3.6 mg is 12-15 days in males and 8-22 days in females. Goserelin 10.8 mg exhibits an initial rapid release resulting in a peak concentration at 2 hours after dosing.

From Day 4 until the end of the 12-week dosing interval, the sustained release of goserelin produces a reasonably stable systemic exposure.

2. Distribution: Apparent volumes of distribution determined after subcutaneous administration of 250 mcg aqueous solution of goserelin were 44.1 and 20.3 liters for males and females, respectively. Goserelin is approximately 27% protein bound.

3. Metabolism: Metabolism of goserelin by hydrolysis of the C-terminal amino acids is the major clearance mechanism. The half-life elimination ($t_{1/2}$) is approximately 4 hours in males and 2 hours in females

4. Elimination: Clearance of goserelin is very rapid and occurs primarily via urinary excretion (>90%; 20% as unchanged drug).

c. ADVERSE EFFECTS

1. Refer to the package insert or manufacturer website for the most complete and up to date information on contraindications, warnings and precautions, and adverse reactions.

Side Effects

Adverse events associated with the use of Leuprolide/Goserelin may include, but are not limited

to, the following:

- hot flashes

- injection site reactions
- weight gain
- increase in liver enzymes
- tiredness
- hypertension
- back and joint pain
- chills
- urinary tract infection
- decreased sex drive and trouble with erectile function

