8.1.1.1. Hematology, Serum Chemistry, and Coagulation Test

Assessments will be performed at the time points indicated in the Schedule of Assessments ([Table](#)) and analyzed at laboratories where collected. Investigators may have additional blood tests performed for the purpose of planning treatment administration, or for following AEs, as clinically indicated.

- Hematology: Complete blood count (CBC) with differential and platelet count.
- Coagulation: Prothrombin time and International Normalized Ratio (INR).
- Serum Chemistry: Total bilirubin, alanine transaminase (ALT), aspartate transaminase (AST), alkaline phosphatase, lipase, amylase, sodium, potassium, bicarbonate, chloride, calcium, phosphorus, blood urea nitrogen, creatinine, magnesium, thyroid stimulating hormone (TSH), and glucose.
- Patients must agree to use effective contraception during the study and for ≥ 180 days following last dose of study drug (Abemaciclib). The definition of effective contraception is provided in [Section 2.6.1](#) of this protocol.

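### Progression requires testosterone recovery, but Table 2 schedules no testosterone after treatment ends, so off-treatment PSA rises cannot be classified from scheduled data

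*Combined protocol and SAP*

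**What the plan says.** The progression rule is in the Synopsis under Overall design: the determination "requires a confirmation of 3 consecutive rises of PSA 3 months apart in the setting of testosterone recovery". It has two parts, a PSA sequence and a testosterone condition.

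Table 2 (Section 4.1.3) has a single testosterone row, "Testosterone level to confirm chemical castration". It is marked at Screening, Cycle 2-3 and Cycle 4 onwards, and is blank at Cycle 1 and at EOT/Follow up. The PSA row, "PSA (at screening, prior to RT, and q month after RT"), is marked in all five columns. CT or MRI is also marked at EOT/Follow up, and its footnote ties the repeat scan to a PSA rise, which it equates with biochemical failure.

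The long-term follow-up text says "Subjects will be followed for survival and subsequent anticancer therapies every 12 weeks", for about 12 months after the end of treatment. For subjects who stop without documented progression or a new anticancer therapy, it adds that "every effort should be made to continue monitoring tumor response status by clinical and radiographic tumor assessments". Testosterone is not mentioned.

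On ADT, a Table 2 footnote reads "LHRH analogues will be administered on C1D1 and continued every 3 months for a maximum of 24 months". Section 6.2 says "Chronic administration of goserelin leads to sustained suppression of pituitary gonadotropins", with testosterone falling to the castrate range.

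**The concern.** The rule needs two results read together, and the schedule stops collecting one of them at about the time it becomes informative. The testosterone row exists to show suppression during ADT; the rule asks about recovery, which the planned regimen makes likely mainly after ADT.

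Follow-up is otherwise set up to detect biochemical failure, with PSA and triggered imaging in the same column. If the plan is followed as written, a PSA rise there is either left unclassified or classified from whatever testosterone was drawn in routine care. Ascertainment would then depend on who happened to be tested. With 23 to 30 patients, a few unclassifiable men could visibly change a Kaplan-Meier curve. Samples never drawn cannot be recovered at analysis.

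**Working it through.** The plan states no figure to reproduce here. The check sets the passages side by side and counts visits.

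**1. What the rule needs.** Three consecutive PSA rises 3 months apart, and recovered testosterone (Synopsis, Overall design).

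**2. What Table 2 schedules.**

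| Column | PSA | Testosterone |
|---|---|---|
| Screening | marked | marked |
| Cycle 1 | marked | blank |
| Cycle 2-3 | marked | marked |
| Cycle 4 onwards | marked | marked |
| EOT/Follow up | marked | blank |

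**3. When recovery is expected.** ADT is given every 3 months to a maximum of 24 months, and Section 6.2 describes sustained suppression. On the planned course, the on-treatment testosterone values therefore fall in the suppressed period. Section 6.4.1 allows ADT doses to be delayed for toxicity, so some earlier recovery is possible.

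**4. Whether another section fills the gap.**
- Section 4.1.3 lists survival, later therapies, adverse events and tumor assessment.
- The serum chemistry panel in Section 8.1.1.1, which is drawn at EOT/Follow up, ends with "magnesium, thyroid stimulating hormone (TSH), and glucose". Testosterone is not among its analytes.
- Appendix 3 recommends testosterone about 8 weeks after ADT starts, and an optional repeat 6 to 12 months after it starts. Both fall within the 24 months of ADT.

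None of these schedules a post-treatment testosterone.

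**5. How many visits are affected.** The safety visit is about 30 days after the last dose, followed by 12-week (84-day) steps to about 12 months (365 days):
- 30
- 30 + 84 = 114
- 114 + 84 = 198
- 198 + 84 = 282
- 282 + 84 = 366

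Four visits fall inside 365 days. The fifth, at day 366, is within the ±28-day window. Scheduled testosterone values: 0 of 4, or 0 of 5.

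**6. Which endpoint is touched.** Section 10.2.2 analyses time to PSA failure by Kaplan-Meier without defining PSA failure. The Synopsis rule is the only PSA-based rule with stated criteria. The primary endpoint in Section 10.2.1 is PSA nadir during treatment and does not use testosterone.

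**The case against.** The strongest reply is that no analysed endpoint is shown to depend on the rule. Progression serves mainly as a reason to stop treatment, at a time when testosterone is scheduled. Time to PSA failure is not said to use the progression rule, and the Table 2 imaging footnote treats a PSA rise as biochemical failure with no testosterone condition. This stands in part: the effect on time to PSA failure is conditional. It does not remove the mismatch, because that footnote gives no number or spacing of rises and so offers no working alternative.

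A reader might also infer more than the documents support:

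- **That follow-up has no scheduled data for the rule, or that PSA follow-up rests on one table mark.** Section 7.1 collects PSA at all study visits, and the Synopsis schedules it every 3 months after radiotherapy. Only testosterone is missing.
- **That recovery is possible only after treatment.** Section 6.4.1 permits ADT delays while on-treatment testosterone is still drawn.
- **That only two PSA sequences fit in follow-up, or that a late first rise is the same fault.** The reference value may be on treatment: a value at day 30 − 84 = −54 followed by rises at days 30, 114 and 198 also fits. Such counts also ignore the visit window. A late first rise is limited by the length of follow-up, and added testosterone would not change that.

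The documents give no time to testosterone recovery, and Section 6.2 describes stable goserelin exposure through a 12-week dosing interval. The first follow-up visit may therefore still be in the suppressed period. That lowers the number of informative visits but leaves the scheduled count at zero.

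**Conclusion.** The mismatch is real and narrow. The stated progression rule needs a testosterone result that the schedule does not collect after treatment, at any of about 4 to 5 visits. Off-treatment PSA rises then cannot be classified under that rule from scheduled data, although the PSA values themselves are scheduled.

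The effect on time to PSA failure holds to the extent that this endpoint uses the Synopsis rule, which the documents neither state nor exclude. Two further assumptions apply: ADT runs broadly as planned, and follow-up visits fall near their nominal days. The point does not reach the primary endpoint or the two-stage decision. It warrants correction because the gap cannot be closed once the visits have passed.

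**What to change.** In Table 2, mark testosterone in the EOT/Follow up column, drawn with each follow-up PSA, including for men who stop treatment early. Extend the row label so that it is no longer confined to confirming castration.

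The sponsor should reconcile the Synopsis rule with Table 2 and state:
- what it counts as testosterone recovery;
- whether time to PSA failure uses the progression rule;
- how a PSA rise without a paired testosterone is handled.

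The recovery definition is the sponsor's to supply; none is proposed here.

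The cost is one added analyte on a draw that Table 2 already schedules, since PSA, hematology and chemistry are marked in that column. That is about 4 to 6 tests per patient (4 to 5 follow-up visits, plus one if an end-of-treatment draw is separate), and a short amendment. The sample size does not change.

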5. SELECTION AND WITHDRAWAL OF PATIENTS

5.1. Patient Inclusion Criteria

1. Histologically confirmed (core biopsy proven) adenocarcinoma of prostate, localized high-risk or locally advanced
2. One of the below:
 - Gleason 7-8, any T-stage, and PSA > 20,
 - Gleason 8, \geq T2, any PSA,
 - Gleason 9-10, any T-stage, any PSA.
 - T3, any Gleason, any PSA
 - Subjects with positive pelvic lymph node(s) are eligible
3. Available biopsy of primary tumor or resected tumor specimen with adequate samples.
4. Prior treatment with systemic anti-cancer agents is not allowed.
5. ECOG PS = 0 or 1
6. Must have at least 1 target lesion
7. Life expectancy > 6 months
8. Adequate hematologic and end-organ function
 - ANC \geq 1500/mm³
 - Platelet count \geq 100,000/mm³
 - Hb \geq 8g/dl
 - Creatinine \leq ULN or Creatinine Clearance (CrCl) \geq 60 ml/min
 - Total Bilirubin \leq 1.5 x ULN (except subjects with Gilbert syndrome, who can have total Bilirubin < 2.x ULN and direct bilirubin within normal limits are permitted)
 - AST and ALT \leq 3.0 x ULN
9. Agreement to remain abstinent or use appropriate contraception.
10. Willingness and ability to consent for self to participate in study.
11. Willingness and ability to comply with scheduled visits, treatment plan, laboratory tests, and other study procedures.

5.2. Exclusion Criteria:

1. Prior treatment with CDK 4/6 inhibitor.
2. Prior treatment with systemic or radiation treatment for the primary cancer.
3. Major surgical procedure or significant traumatic injury within 4 weeks prior to study treatment, and must have fully recovered from any such procedure.
4. Personal history of any of the following conditions: syncope of cardiovascular etiology, ventricular arrhythmia of pathological origin (including, but not limited to, ventricular tachycardia and ventricular fibrillation), or sudden cardiac arrest.
5. Angina, myocardial infarction (MI), symptomatic congestive heart failure, cerebrovascular accident, transient ischemic attack TIA), arterial embolism,

pulmonary embolism, percutaneous transluminal coronary angioplasty (PTCA), or coronary artery bypass grafting (CABG) within 6 months prior to study treatment.

6. Known active viral or non-viral hepatitis or cirrhosis.
7. Any active infection requiring systemic treatment, positive tests for Hepatitis B surface antigen or Hepatitis C ribonucleic acid (RNA).
8. Known history of AIDS (acquired immunodeficiency syndrome)- defining illness.
9. Patients must be surgically sterile or must agree to use effective contraception during the study treatment (including temporary breaks from treatment), and at least 180 days after stopping last dose of Abemaciclib. The definition of effective contraception is provided in [Section 2.6.1](#) of this protocol.
10. Other severe and/or uncontrolled acute or chronic medical or psychiatric condition or laboratory abnormality that, in the judgement of the investigator, may increase the risk associated with study participation or may interfere with the interpretation of study results and would make the patient inappropriate for this study (for example, interstitial lung disease, severe dyspnea at rest or requiring oxygen therapy, severe renal impairment [e.g. estimated creatinine clearance <30ml/min], history of major surgical resection involving the stomach or small bowel, or preexisting Crohn's disease or ulcerative colitis or a preexisting chronic condition resulting in baseline Grade 2 or higher diarrhea).
11. Secondary malignancy requiring active treatment. Past history of malignancy other than prostate cancer treated with curative intent and not requiring additional treatment may be eligible after discussion with PI.
12. Patients with active autoimmune disease and history of inflammatory bowel disease will be excluded. Brachytherapy boost will not be permitted.

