3. TRIAL OBJECTIVES AND PURPOSE

The purpose of this study is to evaluate the safety and tolerability of Abemaciclib in combination with ADT.

Primary Objective:

- To assess clinical response rates using
 - Proportion of patients with PSA nadir of ≤ 0.5 ng/ml on treatment

Secondary Objectives:

- Proportion of patients with PSA declines prior to radiotherapy
- Time to PSA failure
- To study the tolerability and feasibility of combining Abemaciclib with ADT for localized high risk or locally advanced prostate cancer.

Exploratory Objective:

- 1) MRI-US fusion imaging pre-treatment and at 6 months post RT with comparison with historical controls receiving RT + ADT.
- 2) Baseline (mandatory) and 6 months (optional) post RT tumor tissue profiling (MRI-US fusion guided) to identify association of molecular profile with PSA decline at 1 year.
- 3) Baseline, pre-radiotherapy and 6 months post-RT blood collection and profiling for molecular analysis.

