10. STATISTICS

10.1. Statistical Design/Sample Size

Simon's optimal two-stage design (Simon, 1989) will be used for conducting the trial. The null hypothesis is that the proportion of patients with PSA <0.5 without treatment is 5%, and the alternative hypothesis is that the proportion of patients with PSA <0.5 at 6 weeks into treatment is 30% or higher. The trial is carried out in two stages. In stage I, a total number of 5 patients is accrued. If there are 0 response (PSA < 0.5) among these 5 patients, the study will be early stopped. Otherwise, additional 18 patients will be accrued in stage II, resulting in a total number sample size of 23. If there are 4 or more responses (PSA < 0.5) among these 23 patients, we reject the null hypothesis and claim that the treatment is promising. The design controls the type I error rate at one-sided 0.025 and yields the power of 80%. If we reject the null hypothesis, seven additional patients will be enrolled to explore the association between biomarkers and clinical activities. To account for 10% screen failure, total 33 patients will be recruited to the study.

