10.2.1. Analysis of Primary Objective

For each patient, PSA will be measured on systemic treatment with Abemaciclib and ADT after radiotherapy. The primary endpoint is percentage of patients who achieve the PSA nadir levels of \leq 0.5 ng/ml during their treatment. Simon's optimal two-stage design (Simon, 1989) will be used for conducting the trial. The null hypothesis is that the proportion of patient with PSA <0.5 is 5%, and the alternative hypothesis is that the proportion of patient with PSA <0.5 is 30% or higher. The trial is carried out in two stages. In stage I, a total number of 5 patients is accrued. If there are 0 response (PSA < 0.5) among these 5 patients, the study will be early stopped. Otherwise, additional 18 patients will be accrued in stage II, resulting in a total number sample size of 23. If there are 4 or more responses (PSA < 0.5) among these 23 patients, we reject the null hypothesis and claim that the treatment is promising. The design controls the type I error rate at one-sided 0.025 and yields the power of 80%. This response rate will be summarized using both a point estimate and its 2-sided 95% confidence limits.

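### The primary responder rule has no baseline PSA condition, so a man who enters below 0.5 ng/mL counts as a response and can decide the five-patient stage alone

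*Combined protocol and SAP*

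**What the plan says.** **Endpoint.** Section 3 gives the primary measure as "Proportion of patients with PSA nadir of ≤ 0.5 ng/ml on treatment". Section 10.2.1 repeats it as the "percentage of patients who achieve the PSA nadir levels of" 0.5 ng/ml or lower during treatment. Neither asks for a fall from baseline. The hypotheses and decision rule in Sections 10.1, 10.2 and 10.2.1 use a strict <0.5, so Section 10.2.1 contains both signs.

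**Eligibility.** In Section 5.1 one route has a PSA floor: "Gleason 7-8, any T-stage, and PSA > 20". The Gleason 8 with T2 or higher route has none, and neither do "Gleason 9-10, any T-stage, any PSA" and "T3, any Gleason, any PSA". The remaining line in that list, on positive pelvic nodes, sets no PSA limit. No other criterion in 5.1 or 5.2 does so.

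**Analysis set.** Section 10.1.1 defines the efficacy population by tumor measurements and has no baseline PSA condition. By contrast, the secondary endpoint in Section 10.2.2 does compare PSA with baseline.

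**Design.** Section 10.1 takes as its null that "the proportion of patients with PSA <0.5 without treatment is 5"%, with an alternative of 30%. The trial stops if none of the first 5 patients responds, otherwise adds 18, and rejects the null with 4 or more responses in 23.

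**The concern.** A response is meant to show activity. A man already below the threshold when he enters meets the rule unless every on-treatment value is higher than his entry level by enough to cross 0.5. His response then says nothing about treatment, and no rule tells the analyst to set him aside.

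This matters because the counts are very small. One response opens stage II and four declare success. A single such man therefore removes the only futility check, or supplies a quarter of the responses needed. If the case arose, whether to count him would have to be argued after the fact, with the go/no-go decision depending on it.

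The two signs add a smaller ambiguity of the same kind: a nadir of exactly 0.5 is a response under the objective and not under the decision rule.

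**Working it through.** **Inputs** (Section 10.1): n1 = 5, stop at 0 responses; n2 = 18; total 23; reject at ≥4; p0 = 0.05; p1 = 0.30; one-sided limit 0.025; power 80%. Assumption for steps 2 to 4: a man who enters below 0.5 responds with certainty.

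**1. The plan's own design.** P(reject) = Σ over x = 1 to 5 of P(X1 = x) × P(X2 ≥ 4 − x), with X1 ~ Bin(5, p) and X2 ~ Bin(18, p).

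At p = 0.05:
- x = 1: 0.2036 × 0.0581 = 0.0118
- x = 2: 0.0214 × 0.2265 = 0.0049
- x = 3: 0.0011 × 0.6028 = 0.0007
- x = 4 or 5: under 0.0001

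The total is 0.0174. At p = 0.30 the same sum gives 0.806. An exhaustive search under these limits returns this design as Simon's optimal one, so the stated figures reproduce. The chance of passing stage I at the null is 1 − 0.95^5 = 22.6%.

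**2. One entry-low man among the first 5, the other 22 at 5%.** Stage I passes with probability 1. Success then needs 3 or more of the other 22:

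1 − 0.95^22 − 22 × 0.05 × 0.95^21 − 231 × 0.05² × 0.95^20 = 1 − 0.3235 − 0.3746 − 0.2070 = 0.095.

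**3. One such man in each stage, the other 21 at 5%.** Success needs 2 or more of 21:

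1 − 0.95^21 − 21 × 0.05 × 0.95^20 = 1 − 0.3406 − 0.3764 = 0.283.

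**4. One such man in stage II only.** Stage I must still pass unaided, and the total is 0.056.

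| Entry-low men | Pass stage I | Declare success |
|---|---|---|
| none | 22.6% | 1.74% |
| one in stage I | 100% | 9.5% |
| one in stage II | 22.6% | 5.6% |
| one in each stage | 100% | 28.3% |

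These figures are conditional on such men being present. They need no assumed prevalence, but they do not say how often the situation would occur.

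**5. With the fix.** If entry-low men are left out of the decision counts and replaced, and the counted men respond at 5%, the first row applies: 22.6% and 1.74%.

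**The case against.** The strongest reply is that the design already allows for these men. The Synopsis and Sections 10.1 and 10.2 define the 5% null as the rate without treatment, which is the rate at which men sit below 0.5 regardless of drug. If the whole 5% consists of such men, P(reject) is 1.74%, inside the limit. This stands.

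It also rules out several stronger readings that a reader might infer:

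- **That the type I error exceeds 0.025.** Suppose a fraction f of entry-low men comes on top of a 5% response rate in everyone else. Then p = f + (1 − f) × 0.05, which is 5.95%, 6.90% and 9.75% for f = 1%, 2% and 5%, and P(reject) is 3.0%, 4.8% and 12.6%. The documents do not say the men are additional. Section 10.2.1 omits the untreated qualifier but does not say so either. Those figures describe that assumed case only.
- **That a 22.6% chance of an entry-low man in the first five is a defect.** With f set to the plan's 5%, 1 − 0.95^5 is simply the design's own chance of passing stage I under the null.
- **That men after prostatectomy would enter with suppressed PSA.** Section 5.1 accepts a resected specimen ("Available biopsy of primary tumor or resected tumor specimen with adequate samples"), and 5.2 does not expressly bar earlier prostatectomy. But that phrase concerns tissue availability. The plan otherwise describes an intact prostate: core-biopsy proof, a target lesion, definitive radiotherapy and a boost to the prostate.
- **That one such man makes the trial positive.** He cannot, because four responses are needed.

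It is also fair to say that such men should be rare in untreated, biopsy-proven high-risk disease, and that an absolute PSA threshold is a legitimate choice of endpoint. What the reply does not supply is a counting rule for the man who does turn up.

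**Conclusion.** The point holds as a gap in the responder definition. Applied as written, the rule counts a man who enters below 0.5 ng/mL as a response unrelated to the drug. One such man among the first 5 makes passing stage I certain instead of 22.6% at the null. If the other 22 respond at 5%, he raises the chance of declaring success from 1.74% to 9.5%.

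This rests on treating him as a certain responder and on a 5% rate in the others. How often it would happen cannot be worked out from the documents, which give no baseline PSA distribution; probably seldom. No failure of the stated error control is shown. The mismatch between ≤0.5 and <0.5 is a real inconsistency but contributes to none of these figures. Low priority, worth closing because the decision counts are so small.

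**What to change.** In Sections 10.1 and 10.2.1:

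- Count only patients whose baseline PSA is above 0.5 ng/mL in the 5- and 23-patient decisions. Name which pre-dose value is the baseline, since the Schedule of Assessments has PSA at both screening and Cycle 1 Day 1. Patients at or below 0.5 stay in the safety population and are replaced in the decision counts. As the condition is known before treatment, replacement does not depend on outcome.
- Use one threshold sign in the objectives, hypotheses and decision rule, and carry it into the Synopsis and Section 4.1.1.
- Restate what the 5% null represents. Once entry-low men are excluded, the proportion below 0.5 without treatment is close to zero by construction, so the present description no longer fits and the 5% needs its own justification.

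Cost: no new data, because PSA is already drawn at those visits. A rare patient may need replacing, which could delay the stage I decision slightly. The null wording has to be rewritten, so this is more than a one-sentence edit.
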